Clinical Research Protocol

Title: Clinical study of CLDN 18.2-targeting chimeric antigen receptor-modified autologous T cells for CLDN 18.2-positive advanced solid tumors

Protocol No.: IMC002-CT01

Version: V2.0

Version date: 2022-01-25

Protocol synopsis

Title: Clinical study of CLDN 18.2-targeting chimeric antigen receptor-modified autologous T cells for CLDN 18.2-positive advanced solid tumors.
Protocol No.: IMC002-CT01
Version and date: Version 2.0; January 25, 2022
Type of study: IIT study (investigator-initiated trial)
Research Centers: 3
Investigational drug: chimeric antigen receptor-modified autologous T cells targeting CLDN 18.2 (hereinafter referred to as "CLDN 18.2 CAR-T" or "CAR-T" cells), codenamed IMC002 Dosage form and specification: Injection, $5 \times 10^7 \sim 3.5 \times 10^8$ CAR-T positive live cells
Mode of administration: Intravenous infusion
Indications: Advanced solid tumors with positive CLDN18.2 expression (including advanced gastric cancer/gastroesophageal junction cancer, advanced pancreatic cancer, and advanced ovarian cancer).
Number of cases: 10 to 30 cases
Research objectives Primary objective: 1) To observe and evaluate the safety and tolerability of advanced solid tumors patients with positive CLDN18.2 expression treated with intravenous infusion of IMC002. Secondary objectives: 1) To determine the maximum tolerated dose (MTD) and recommended phase II dose (RP2D) according to dose-limiting toxicity and clinical response including possible side effects after IMC002 treatment of advanced solid tumors patients with positive CLDN18.2 expression.

- 2) To evaluate the correlation of pharmacodynamic (PD) biomarkers with clinical efficacy to IMC002; the correlation of in vivo expansion and persistence of IMC002 and pharmacodynamic (PD) biomarkers and adverse events.
- 3) To evaluate the preliminary antitumor efficacy of IMC002 in patients with advanced solid tumors with positive CLDN18.2 expression using objective response rate (ORR), duration of response (DOR), disease control rate (DCR) and progression-free survival are used Phase (PFS) according to Response Evaluation Criteria in Solid Tumors (RECIST1.1), Immunotherapy Response Evaluation Criteria in Solid Tumors (iRECIST).
- 4) Incidence of treatment-related adverse events.

Exploratory Purpose:

- 1) To assess changes in immune status after IMC002 treatment.

Study design:

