Secondary endpoints: Engraftment endpoints after infusion of IMC002 (CLDN 18.2 CAR-T cells), i.e., copy number and sustained survival time of cells in vivo.

The “engraftment endpoint” is defined as the number of copies of CLDN 18.2 CAR-T DNA in peripheral blood detected by q-PCR at each visit point from the end of the infusion until any 2 consecutive test results are negative or below the detection limit. The time from the day of infusion to the first negative result or below the lower limit of detection is recorded as the survival time of IMC002 (CLDN 18.2 CAR-T cells).

Safety endpoints: The incidence of DLT is assessed according to NCI CTCAE 5.0 and its correlation with investigational product, lymphodepletion and leukopheresis.

Other safety endpoints:

- The type, incidence, and severity of adverse events, including abnormal clinically significant laboratory test results, abnormal physical examination and blood test results, bone marrow test results, and immunogenicity results after treatment. AE/SAE is assessed according to NCI CTCAE version 5.0. The association of adverse events with the IMC002 CAR-T treatment regimen will be assessed by the investigator according to the attribution evaluation criteria specified by the protocol.
- Grade 3-4 laboratory tests and their association with investigational products, lymphodepletion, and leukopheresis.

Efficacy evaluation endpoints:

Efficacy is evaluated using RECIST1.1 and iRECIST1.1. For each subject, the same technique must be used to obtain tumor imaging during the trial. For subjects first determined to be in complete remission (CR) or partial remission (PR), the assessment results should be confirmed by repeat imaging scans at least 4 weeks later.

Efficacy endpoints include tumor objective response rate (ORR), disease control rate (DCR), duration of response (DOR), progression-free survival (PFS), and overall survival (OS).

Objective response rate (ORR) is defined as the proportion of subjects with confirmed response as CR or PR; tumor response status is assessed by investigators according to Response Evaluation Criteria in Solid Tumors (RECIST1.1).

Duration of response (DOR) interval from first assessment as CR or PR to first assessment as PD or death from any cause (percentage of subjects with DOR ≥ 24 weeks, ≥ 36 weeks, ≥ 48 weeks will be reported).

Disease control rate (DCR) percentage of patients who confirmed as CR or PR or SD (RECIST1.1).

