Descriptive statistical analysis is performed on the indicators, and median Tmax, Cmax, as well as the survival rate and cell number of CAR-T cells in peripheral blood within 96 weeks after IMC002 infusion are provided. The relevant parameters should be analyzed separately for responders and non-responders and compared. Descriptive statistical analysis is performed on the cytokine dose-response relationship, and the median peak value of each cytokine within 4 weeks of CAR-T cell infusion, and the median time to return to baseline or normal range are provided.

The differences in the dose-response relationship of patients in different dose groups are compared.

Ethics:

The protocol (including the informed consent form) must be approved by an independent ethics committee before start. This study strictly follows the protocol and GCP to fully protect the legitimate rights and interests and safety of the subjects.

Research period: Expected from December 2021 to December 2024

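### CAR-T survival time is dated to the first negative q-PCR result without tying that result to the two consecutive negatives that end the measurement

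*Protocol*

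**What the plan says.** Under *Study endpoints and evaluation indicators*, the Protocol names as secondary endpoints "copy number and sustained survival time of cells in vivo". Two adjacent sentences then define the engraftment endpoint.

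- The first sets how long the cells are measured: CAR-T DNA copies in peripheral blood at each visit, "until any 2 consecutive test results are negative or below the detection limit".
- The second dates the survival time: the interval from the day of infusion "to the first negative result or below the lower limit of detection is recorded as the survival time".

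Persistence is used in two other places. *Research objectives* lists as secondary "the correlation of in vivo expansion and persistence of IMC002 and pharmacodynamic (PD) biomarkers and adverse events". *Statistical analysis of dose-response relationship* says that median Tmax and Cmax, "as well as the survival rate and cell number of CAR-T cells in peripheral blood within 96 weeks after IMC002 infusion are provided", and adds: "The relevant parameters should be analyzed separately for responders and non-responders and compared".

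Nothing else in the Protocol links the measurement rule to the dating rule, or says how to treat a negative that is followed by a positive.

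**The concern.** Under the first sentence a single negative does not stop the measurement; two in a row are needed. Under the second, taken at its word, that single negative already fixes the survival time. A subject can therefore have a completed survival time while the same endpoint is still recording positive copy numbers.

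This can happen in two ways. A sample taken soon after infusion may fall below the limit before the cells expand; the recorded survival time would then be shorter than the time to peak, which the Protocol reports separately under *Metabolic kinetic endpoints*. Or one negative may occur later, between positives.

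At stake is the value of a named secondary endpoint and the correlations of persistence with PD biomarkers and adverse events. Two programmers could also code the sentence differently, and both could claim to follow the Protocol. With 10 to 30 subjects planned, a few misdated values can move a median.

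**Working it through.** **No figure to reproduce.** The Protocol gives no number on this point. The check sets the two rules side by side and then sizes the gap under stated assumptions.

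**Step 1: one series under both rules.** This series is invented for illustration: positive on days 7 and 14, negative on day 21, positive on days 28 and 56, negative on days 84 and 112.

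- Literal rule, first negative: 21 days, although copies are still detected on days 28 and 56.
- First of the consecutive pair: 84 days.

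If the first negative is at once followed by a second, the two rules give the same date. They differ only when a negative is followed by a positive.

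**Step 2: inputs, all assumed.**

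- k = number of q-PCR visits while cells are still present: 8 or 4.
- q = chance of a negative or below-limit result at each such visit: 5%, 10% or 20%.
- Results are independent between visits, and every result from visit k+1 on is truly negative.

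**Step 3: literal rule.** Survival time ends too early if any of the k results is negative:

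P(literal) = 1 − (1 − q)^k

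For k = 4 and q = 0.10: 1 − 0.9^4 = 0.344.

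**Step 4: pair rule.** This rule can also end too early, in two ways: two negatives in a row within the k visits, or a negative at visit k that pairs with the true negative at visit k+1. Let a be the probability of no pair so far with the last result positive, and b that of no pair so far with the last result negative. Start at a = 1, b = 0 and update at each visit:

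a′ = (a + b)(1 − q), b′ = a·q

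P(pair) = 1 − a after k visits.

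For k = 4 and q = 0.10, a runs 0.9, 0.9, 0.891, 0.8829, so P(pair) = 0.117. The excess due to the wording is 0.344 − 0.117 = 0.227.

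**Step 5: results.**

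| k | q | Literal rule ends early | Pair rule ends early | Excess |
|---|---|---|---|---|
| 8 | 5% | 33.7% | 6.4% | 27 points |
| 8 | 10% | 57.0% | 14.9% | 42 points |
| 8 | 20% | 83.2% | 35.5% | 48 points |
| 4 | 5% | 18.5% | 5.5% | 13 points |
| 4 | 10% | 34.4% | 11.7% | 23 points |
| 4 | 20% | 59.0% | 25.8% | 33 points |

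The last column is the part that belongs to the wording. The literal column alone overstates it, because it includes early negatives that the pair rule would date identically or would also take as the end.

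**The case against.** **The natural reading is the first of the pair.** The sentences are adjacent, and read in sequence the second may simply refer back to the two consecutive results. The document looks like a translation (some table captions are still in Chinese), so a dropped reference is plausible. This stands as a likely account of the intent. It does not settle the text, which states an explicit dating rule and does not limit it to the pair.

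**The two rules govern different things.** One ends the copy-number series and the other dates survival time, and the Protocol gives no reason for asking for two negatives. That is correct: a reader might infer that the Protocol declares a single negative not to be loss of cells, but it never says so. The difficulty needs no such statement. A survival time that ends before later positive results is at odds with those results.

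**Little depends on it.** This largely stands. The main indicators under *Metabolic kinetic endpoints* are peak, time to peak and AUC0-28, and none of them uses the survival time. A reader might infer that the misdating enters a correlation of persistence with efficacy. The objectives do not say that: they correlate PD biomarkers with efficacy, and persistence with PD biomarkers and adverse events. The responder comparison is the nearest link, but the parameters it lists include a survival rate and cell number, not survival time.

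**The size rests on assumptions.** This also stands. A constant, independent rate has no support in the Protocol. If below-limit results cluster just before true loss, the time lost would be small.

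**Conclusion.** The point holds as a defect of definition. As worded, the survival time is wrong for any subject with a negative followed by a positive, and no other text in the Protocol corrects it. Under the assumptions above, the wording cuts survival time short in about 27, 42 or 48 more subjects per 100 than the pair rule with 8 visits, and in 13, 23 or 33 more with 4. These figures show the possible range; they are not estimates for this trial, because the isolated-negative rate and the visit count are not given.

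Two stronger readings are not supported. One is that 34%, 57% or 83% of subjects would be misdated because of the wording (8 visits): those are the chances of any negative at all, and part of that remains under the pair rule. The other is that the main result is at risk: DLT, MTD and dose escalation do not use this endpoint. The consequence is limited to one secondary measure and its correlations with PD biomarkers and adverse events, so this is a minor but worthwhile correction.

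**What to change.** Replace the dating sentence with:

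> Survival time is the time from the day of infusion to the first of the two consecutive negative or below-limit results that end the measurement; subjects without such a pair are censored at their last sample.

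The first clause is the correction. The censoring clause completes the definition; a SAP could hold it instead, and its absence from the Protocol is not counted as a fault here.

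Do not add a condition that no later result be positive. The Protocol defines the measurement only up to the two consecutive negatives, so later samples need not exist.

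The cost is one sentence, with no new samples or visits. The pair rule is not free of error, as the table shows, but it agrees with the Protocol's own end of measurement and leaves one way to program the endpoint.

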Imaging assessments are based on RECIST1.1 until confirmed disease progression.

Pseudoprogression may occur with IMC002 treatment due to infiltration of IMC002 autologous CAR-T cells or other mechanisms resulting in a significant increase in existing tumor volume. If the investigator suspects pseudoprogression of disease according to RECIST1.1, the assessment should be confirmed by repeat imaging after at least 4 weeks (no later than 8 weeks). The criteria for confirming progression are on the basis of the imaging results of the last suspected progression, the sum of the target lesion measurements has further increased by at least 5 mm, or the progression of non-target lesions, or the number of new lesions has further increased or increased in number. If the efficacy assessment reaches CR, PR, and SD compared with the baseline according to the RECIST1.1, the previously suspected

progression cannot be confirmed; as long as the suspected progression is not confirmed, subsequent imaging examinations can be performed for confirmation.

Statistical Analysis:

All statistical analyses will be done with SAS 9.4 or above. In general, continuous variables will be described using the number of cases, mean, median, standard deviation, minimum and maximum values; categorical and rank variables will be statistically described using frequencies and percentages for each category or rank; missing values are not included in the calculation of percentages unless otherwise stated. All statistical tests will use a two-sided test with $\alpha=0.05$, and a two-sided 95% confidence interval (CI) will be calculated.

Demographics and other baseline characteristics

Demographic data and other baseline characteristics are summarized using descriptive statistics.

Analysis of safety indicators

The primary safety endpoint of this study is the DLT observed at 28 days post-infusion, which will be used to determine the MTD.

All adverse events after infusion will be performed in the safety analysis population.

Efficacy endpoints analysis

According to the RECIST1.1, the progression-free survival (PFS) and overall survival (OS) of each dose and all patients within 96 weeks after IMC002 treatment are evaluated, and 12 months after IMC002 infusion will be counted and calculated. PFS and OS are achieved within the period, and their bilateral 95% exact confidence intervals are calculated to analyze the dose-efficacy relationship.

Statistical analysis of dose-response relationship

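### When pseudoprogression is suspected, the confirming and cancelling clauses use different reference scans with no stated precedence, so one scan of a responder regrowing from nadir can satisfy both

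*Protocol*

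**What the plan says.** All of the following is in the protocol synopsis.

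- **Trigger** (Tumor efficacy evaluation): "If the investigator suspects pseudoprogression of disease according to RECIST1.1, the assessment should be confirmed by repeat imaging after at least 4 weeks". The upper limit for the repeat scan is 8 weeks. The procedure is tied to a suspicion of pseudoprogression, not to every progression.
- **Confirming clause** (same section): the comparison is made "on the basis of the imaging results of the last suspected progression", and it is met if "the sum of the target lesion measurements has further increased by at least 5 mm, or the progression of non-target lesions", or if new lesions grow or become more numerous.
- **Cancelling clause** (the next sentence): "If the efficacy assessment reaches CR, PR, and SD compared with the baseline according to the RECIST1.1", then the previously suspected "progression cannot be confirmed; as long as the suspected progression is not confirmed, subsequent imaging examinations can be performed for confirmation".
- **DOR** (Efficacy evaluation endpoints): runs from "first assessment as CR or PR to first assessment as PD or death from any cause". The percentages of subjects with DOR of at least 24, 36 and 48 weeks are to be reported.
- **PFS** (same section): runs from first infusion to progression or death. It does not say whether the suspected or the confirmed progression date counts.
- **Follow-up**: RECIST 1.1 assessment continues up to confirmed progression, and imaging stops at week 96 at the latest. Response is assessed by the investigators, at 3 centers.

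**The concern.** The two clauses answer the same question, whether this progression is confirmed, against different scans. The confirming clause looks back to the suspected scan and the cancelling clause looks back to baseline. RECIST 1.1 measures progression from the smallest sum on study, so a subject who shrank well and is now regrowing can be progressing by that standard while still well below baseline. The subjects most exposed are the responders, who supply the DOR estimate and much of the efficacy signal.

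The consequence is inconsistent classification. With no order of precedence, two sites can apply the text in good faith and record opposite results from identical images. With 10 to 30 subjects in total, one or two responders classified differently can visibly move the DOR percentages. If the cancelling clause is the one followed, and the confirmed date is the one analysed, the error runs in one direction, towards longer DOR and PFS.

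**Working it through.** The plan gives no figure on this point to reproduce, so the check applies both clauses to the same scan.

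**Assumptions (not printed in the protocol).** PR is a sum at least 30% below baseline. PD is a sum at least 20% and at least 5 mm above the reference, which is the nadir in RECIST 1.1. Only target lesions change.

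**Step 1: one worked subject.** Baseline 100 mm, nadir 50 mm, suspected progression 62 mm, repeat scan 69 mm.

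- Response at nadir: 50/100 − 1 = −50%, so PR.
- Suspected progression against nadir: 62 − 50 = +12 mm, and 12/50 = +24%, so PD.
- Confirming clause, repeat against suspected scan: 69 − 62 = +7 mm, which is at least 5 mm. **Confirmed.**
- Cancelling clause, repeat against baseline: 69/100 − 1 = −31%, so PR. **Cannot be confirmed.**
- Repeat against nadir, for reference: 69 − 50 = +19 mm, and 19/50 = +38%, so PD.

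**Step 2: how general is the overlap?** Let B be baseline and N nadir. Take the smallest growth that triggers and confirms: S = max(1.2N, N + 5) and C = S + 5 mm. Then read C against B.

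| B (mm) | N (mm) | S (mm) | C (mm) | C against baseline |
|---|---|---|---|---|
| 100 | 40 | 48 | 53 | −47%, PR |
| 100 | 70 | 84 | 89 | −11%, SD |
| 100 | 100 | 120 | 125 | +25%, PD (no overlap) |
| 17 | 11.9 | 16.9 | 21.9 | +4.9 mm, SD |
| 15 | 10.5 | 15.5 | 20.5 | +5.5 mm, PD (no overlap) |

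At this minimum growth, every responder (N at most 70% of B) with a baseline sum of about 17 mm or more meets both clauses. A subject whose nadir is the baseline does not. Faster growth shrinks the overlap, because the repeat scan may already be PD against baseline.

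**Step 3: size if the cancelling clause prevails.** On target growth alone, the sum must then reach 120% of baseline before confirmation is possible. Under steady exponential growth, the time from nadir relative to ordinary PD is ln(1.2 ÷ (N/B)) ÷ ln(1.2).

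- N/B = 0.5: ln(2.4)/ln(1.2) = 0.875/0.182 = 4.8 times as long.
- N/B = 0.7: ln(1.714)/ln(1.2) = 0.539/0.182 = 3.0 times as long.

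In weeks, with B = 100 and N = 40 mm, growth of 30% down to 10% per scan, and an assumed scan interval of 4 or 8 weeks, the time from first PD until the cancelling clause stops applying is:

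- 4-week scans: 16 to 40 weeks.
- 8-week scans: 32 to 80 weeks.
- Both intervals, with the cut-off for PD against baseline varied from 10% to 30%: 12 to 88 weeks.

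Delays of this length could carry a subject across the 24-, 36- or 48-week DOR landmarks, and slow growth could run to the week-96 end of imaging.

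**The case against.** The strongest reply is that the cancelling clause also invokes RECIST 1.1. A reader who applies that system in full would call the 69 mm scan PD from the nadir (+38%), so the scan would never reach CR, PR or SD and the clause would not apply. This stands as a possible reading. It does not remove the problem, because the same clause names baseline as the comparison. Two defensible readings of one scan are the defect.

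A reader might infer more: that every relapsing responder has progression dated late or never. The documents do not support that, for these reasons.

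- The procedure starts only when pseudoprogression is suspected, so many relapses never enter it.
- Relapse through new or non-target lesions would not normally read as CR, PR or SD. The overlap mainly concerns target-lesion growth.
- DOR ends at the first assessment as PD and does not mention confirmation. No passage says that the confirmed date enters DOR or PFS.
- Later scans may still confirm, and death ends both endpoints.

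A reader might also infer that the withdrawal reason based on confirmed progression is blocked. It is not. The list under Withdrawal criteria is discretionary, that item refers to iRECIST, and other reasons remain available.

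Finally, the choice of event date is often left to a statistical analysis plan, which is not shown here. That is fair for the date alone. It does not cover two conflicting rules that investigators apply scan by scan, because an analysis plan cannot easily undo what the sites have already classified.

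**Conclusion.** The concern holds in a limited form. For subjects in whom pseudoprogression is suspected, two adjacent sentences use different reference scans without precedence, and a responder regrowing from nadir on target lesions can meet both on the same scan. Classification can then differ between sites.

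The existence of the overlap rests on the assumed standard cut-offs and on reading the baseline reference literally. Its effect on DOR and PFS rests on two further conditions: that the cancelling clause is followed, and that the confirmed date is analysed. The 3.0 and 4.8 ratios and the 16 to 80 weeks are therefore a conditional worst case under assumed growth and scan intervals, not an expected bias.

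Severity is moderate. Only secondary efficacy endpoints of a dose-escalation study are affected; the 28-day DLT/MTD primary endpoint is not.

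**What to change.** Reconcile the two sentences under Tumor efficacy evaluation, for endpoint assessment:

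1. State that the confirming criteria are tested first. The CR/PR/SD clause applies only if none of them is met and the scan is not PD against the smallest sum on study.
2. State that a confirmed progression is dated at the first suspected scan, for both DOR and PFS. This agrees with the existing DOR definition, which ends at the first assessment as PD.

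A scan that meets no confirming criterion but is still PD against the nadir stays open under the existing provision for further imaging.

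The cost is two sentences and no extra scans. DOR and PFS may be shorter for some responders than under the baseline reading.

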Before lymphodepletion and 3 days before IMC 002 infusion, if the investigator judges that the subject has significant abnormalities; or the investigator judges that the subject has rapid disease progression compare to the screening time; or the investigator assesses that the patient has significant organ dysfunction (such as severe heart disease, uncontrollable hypertension or diabetes, severe liver or kidney damage, pulmonary edema, severe lung infection, brain metastasis); and it is not suitable for follow-up test procedures, then the lymphodepletion cannot be continued or should be delayed; the CAR T cells should not be infused or the infusion should be delayed.

If the infusion of cells is delayed for more than 5 days after lymphodepletion for any reason, the infusion is not allowed or needs to be delayed.

Withdrawal criteria:

- Subjects may withdraw from the study at any time of their choice.
- Subjects who did not complete the study protocol, including cell infusion and follow-up assessments, are considered to have terminated the study early.
- The reason for termination must be recorded in the CRF and maintained for the specified period of time as required by GCP.
- Subjects may be withdrawn from the study at any time during the study at the discretion of the investigator for reasons of subject safety, behavior, or management reasons, including:
 - 1) Disease progression confirmed by imaging and iRECIST criteria.

- 2) The cumulative treatment reached 96 weeks (no radiographic progression).
- 3) The subjects experienced serious adverse reactions.
- 4) Subject died.
- 5) Subject is pregnant.
- 6) Major protocol deviation included, but not limited to:
 - a) Mistaken for failing to meet inclusion/exclusion criteria
 - b) Concomitant use of prohibited drugs in this protocol
 - c) The subjects did not cooperate with the treatment and follow-up, are lost to the follow-up, or the subjects did not come to the hospital for more than two follow-up visits on time.
- 7) The disease progressed rapidly before the cell infusion, and the investigators determined that other treatment regimens needed to be used based on the maximum benefit of the subjects.
- 8) In the absence of efficacy, the investigator determined that the subject did not benefit from the trial treatment, and continued participation in the study may put the patient at unacceptable risk.

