Progression-free survival (PFS) is defined as the time interval from the subject's first infusion of IMC002 to disease progression or death from any cause, whichever occurred first. For subjects with no documented disease progression or death, the cutoff date is the date of the last examination.

Overall survival (OS) is defined as the time interval between subjects receiving the first infusion of IMC002 and the recording of death from any cause. For subjects whose death is not recorded, subjects who did not die by the analysis cut-off date are censored with the last contact time.

For subjects with advanced solid tumors with positive CLDN18.2 expression, after 4 weeks of treatment, the treatment effect of the target lesions is evaluated using the RECIST1.1 and iRECIST1.1: treatment effect = (CR+ PR)/total number of cases × 100%.

Metabolic kinetic endpoints:

The expansion and persistence of CLDN 18.2 CAR-T cells in peripheral blood will be detected by q-PCR. The main evaluation indicators: peak CAR-T cells (the highest number of CAR+ peripheral blood mononuclear cells in serum after cell infusion), Time to peak (days after cell infusion to peak CAR-T cells) and AUC0-28 (area under the curve plotted from days 0 to 28 as the number of CAR-T cells in serum versus visit time).

Exploratory endpoints:

Detection of cytokine levels in blood before and after treatment, including but not limited to pro-inflammatory and immunomodulatory cytokines IL-6, TNF α , IL-8, IL-1 α , IL-10, IL-12, IL-2R α , GM-CSF, IL-15, IFN γ , immune effector molecule granzyme B, acute phase response-related factors CRP, Ferritin, VCAM-1, and chemokines MCP-1, IP-10.

The level of ADA in blood will be detected before and after treatment.

Explore the correlation of biomarkers with efficacy and safety.

Tumor efficacy evaluation:

During the screening period, imaging (unenhanced and enhanced nuclear magnetic resonance MRI or CT, the specific examination site shall be determined by the investigator according to the patient's condition) and tumor markers should be examined. The imaging results 28 days before cell infusion can be set as study baseline. Imaging (unenhanced and contrast-enhanced MRI or CT) and tumor markers are then performed at the scheduled visits of the study protocol until Week 96, disease progression, subject lost to follow-up, withdrawal of informed consent, or death (whichever occurs first).

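### PFS and OS are defined as censored times, but their 12-month rates appear to be simple counts with exact intervals, which are biased if anyone is censored before month 12

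*Protocol*

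**What the plan says.** All references are to the protocol synopsis.

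- **Endpoint definitions (Efficacy evaluation endpoints).** For PFS: "For subjects with no documented disease progression or death, the cutoff date is the date of the last examination". For OS: "subjects who did not die by the analysis cut-off date are censored with the last contact time". Both are therefore censored times to event.
- **Analysis (Statistical Analysis, Efficacy endpoints analysis).** PFS and OS are evaluated over 96 weeks for each dose and for all patients. The text then turns to month 12: "12 months after IMC002 infusion will be counted and calculated". It continues: "PFS and OS are achieved within the period, and their bilateral 95% exact confidence intervals are calculated to analyze the dose-efficacy relationship". The protocol names neither Kaplan-Meier nor any other method that uses censored follow-up.
- **General rule (Statistical Analysis, opening paragraph).** For descriptive percentages, "missing values are not included in the calculation of percentages unless otherwise stated". Nothing different is said about the 12-month rates.
- **How follow-up can end (Tumor efficacy evaluation).** Imaging and tumor markers continue "until Week 96, disease progression, subject lost to follow-up, withdrawal of informed consent, or death (whichever occurs first").

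**The concern.** The definitions provide for censoring, and the analysis sentence does not use it. Counting who reached 12 months, with an exact interval, treats each subject's 12-month status as a known yes or no. A subject who leaves at month 5 without progression has no such status. The analyst must drop that subject, call the subject a success, or call the subject a failure. None of the three recovers the true rate, and the text does not choose among them.

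The stated use is the dose-efficacy relationship. Two analysts who both follow the text could report different 12-month rates from the same 10 to 30 subjects. The partial follow-up of censored subjects would also be wasted in a small trial.

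**Working it through.** The protocol gives no 12-month rate and no dropout rate, so there is no figure of its own to reproduce. The inputs below are assumptions.

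**Inputs.** True 12-month event-free rate S = 20%, 40% or 60%. Dropout d by month 12 (the share who would be censored if there were no events) = 10%, 20% or 40%. Event and dropout times are exponential and independent.

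**Formulas.** With yearly rates a = -ln(S) and b = -ln(1-d):

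- P(event seen by month 12) = a/(a+b) × [1 - S(1-d)]
- P(censored before month 12) = b/(a+b) × [1 - S(1-d)]
- P(event-free and observed at month 12) = S(1-d)

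The three possible counts are:

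- excluded: S(1-d) / [S(1-d) + P(event)]
- counted as event-free: S(1-d) + P(censored)
- counted as failures: S(1-d)

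**Worked case, S = 40%, d = 20%.** a = 0.916, b = 0.223, S(1-d) = 0.320.

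- P(event) = 0.804 × 0.680 = 0.547
- P(censored) = 0.680 - 0.547 = 0.133
- Excluded: 0.320 / (0.320 + 0.547) = 0.369
- Event-free: 0.320 + 0.133 = 0.453
- Failures: 0.320

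In 30 subjects this is an expected 16.4 events, 4.0 censored and 9.6 event-free. Exclusion gives 9.6/26.0 = 36.9%.

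**Other settings**

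| True rate | Dropout | Excluded | Counted event-free | Counted failures |
|---|---|---|---|---|
| 40% | 10% | 38.5% | 43% | 36% |
| 40% | 20% | 36.9% | 45% | 32% |
| 40% | 40% | 33.0% | 51% | 24% |
| 20% | 20% | 17.8% | 26% | 16% |
| 20% | 40% | 15.2% | 33% | 12% |
| 60% | 20% | 57.0% | 64% | 48% |
| 60% | 40% | 52.9% | 68% | 36% |

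**Comparison with Kaplan-Meier (simulation, n = 30, true 40%, dropout 20% / 40%).** The mean Kaplan-Meier rate is 39.9% / 40.0%. Its log-log interval covers 95% / 95%, with mean width 35 / 38 points. The exact interval after exclusion covers 96% / 94%, with mean width 38 / 41 points. So the main fault lies in the rate, and coverage is little affected.

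**Scale.** Exact intervals run from 12% to 74% for 4/10 and from 23% to 59% for 12/30. A shift of about 3 points (40% to 36.9%) is small beside either.

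**The case against.** A reader might infer that the 12-month rates will be biased downward, because the general rule removes missing values from percentages and would remove early-censored subjects while keeping early events. The protocol does not support this as a statement of fact. It never calls a censored subject missing, and its definitions give such a subject a time. The missing-value rule sits in a general sentence on describing categorical variables and yields to anything stated otherwise. Exclusion is one possible handling; counting the same subjects as event-free reverses the direction.

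A reader might also infer that the comparison between doses is distorted. That needs dropout that differs by dose, or a cut-off before the latest dose groups reach 12 months. With 0% dropout in one group and 40% in another, exclusion gives 40% against 33%. With one group of 10 followed for an assumed 6 to 18 months, exclusion gives 27% against a true 40%. Nothing in the protocol indicates either situation. The research period is "Expected from December 2021 to December 2024", so within it a cut-off problem arises only if first infusions continue after December 2023 or the cut-off is brought forward.

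Three further objections have weight:

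- The sentence is garbled, and a binomial count is only its most natural reading.
- Handling of censored subjects is often left to a SAP. The protocol, however, goes further than silence: it specifies counting and exact intervals, and none of the three simple counts of all subjects is right once anyone is censored early.
- The OS half has less support. The clause on loss to follow-up and withdrawal of consent concerns imaging and tumor markers and does not say that survival contact stops. Several listed withdrawal reasons also cannot censor PFS before month 12: progression and death are events, and 96 weeks falls later.

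**Conclusion.** The point holds as an inconsistency between the endpoint definitions and the analysis sentence, and it is worth correcting. On its natural reading, the 12-month analysis counts proportions of censored times. The count is biased whenever a subject is censored before month 12, in a direction that depends on a handling the protocol does not fix. At a true 40% and an assumed 20% dropout, the three handlings span about 13 points (32% to 45%); exclusion alone shifts the rate by about 3 points.

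The weight is modest. PFS and OS are not primary, MTD selection rests on DLT data, no stated decision rule uses these rates, and sampling error dominates at 10 to 30 subjects. If every 12-month status is known, there is no bias. The sizes rest on assumed dropout rates and on independent exponential times. A definite downward bias, or a distorted dose comparison, is not established.

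**What to change.** In Efficacy endpoints analysis, replace the counted rates and exact intervals with:

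> PFS and OS will be estimated by the Kaplan-Meier method, overall and by dose, with 12-month rates and two-sided 95% log-log CIs. Subjects without an event are censored as defined and are not treated as missing. Where a dose group is too small or the interval is undefined, individual times, censoring and reasons for censoring will be listed.

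If a counted proportion is preferred, take as denominator all subjects infused at least 12 months before the cut-off, with or without an event, and state how dropouts are handled. This removes cut-off bias but leaves dropout bias.

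The cost is wording only; the method is standard in the named software. There are two downsides. First, the log-log interval is often undefined in small groups: always at n = 1 and, at a true 40% with 20% / 40% dropout, in about 35% / 41% of runs at n = 3, 9% / 14% at n = 6 and 2% / 4% at n = 10. In groups of 1 to 3 subjects only the listings are informative. Second, Kaplan-Meier assumes censoring unrelated to prognosis, while the withdrawal criteria include this ground: "In the absence of efficacy, the investigator determined that the subject did not benefit from the trial treatment". That is why the reasons for censoring should be listed.
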